**Table 1: Dose Modification Schedule and Rules Through Study Day 85**

Study Day	Dose and Requirements for Dose Modification
1	Initiate dosing at 5 mg twice daily
15	At Day 15, dose will be increased to 10 mg twice daily if all of the following are true: 
 
• Subject has not achieved and maintained at least Partial Remission and
 
• Subject is not a Treatment Failure
 

29	At Day 29, PK samples will be collected to measure AUC 0-6 and enable projection of AUC 0-12 at both the current dose level and the next higher planned dose level AUC 0-12
43	At Day 43 based on results of the Day 29 PK, the dose may be adjusted to the next higher planned dose level (15 mg twice daily for subjects receiving 10 mg twice daily; 10 mg twice daily for subjects receiving 5 mg twice daily) if all of the following are true: 
 
• Subject is not a Treatment Failure, and
 
• Meets all criteria for continuation:               
 
○ Subject has not achieved and maintained at least a Partial Remission, and
 
○ Projected AUC0-12 on the next higher planned dose level does not exceed 240 <math>\mu\text{g}\cdot\text{h}/\text{mL}</math> and
 
○ The next higher dose does not exceed the Maximum Tolerated Dose (MTD)
 
 
 
 NOTE: If the projected AUC 0-12 on the current dose exceeds 240 $\mu\text{g}\cdot\text{h}/\text{mL}$ , dose will be de-escalated to the next lower dose level
57	At Day 57, PK samples will be collected to measure AUC 0-6 and enable projection of AUC 0-12
Day 71	Based on results of Day 57 PK, subjects can be considered for dose escalation if all of the following are true: 
 
• Subject is not already treated with 15 mg twice daily and
 
• Subject did not require previous downward dose adjustment and
 
• Subject is not a Treatment Failure, and
 
• Meets all criteria for continuation:               
 
○ Subject has not achieved and maintained at least a Partial
 
 
 

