## Dose Modification Rules

### **Dose Modification Rules for individual subjects**

Discontinue treatment with CCX140-B when a subject experiences any of the following events confirmed by repeat measurement after 2 weeks:

- Progression of renal disease, defined as eGFR that is both below 60 ml/min/1.73  $m^2$  and is confirmed to represent at least 30% decline in eGFR from baseline
- Requirement for rescue with glucocorticoids, other new immunomodulatory or immunosuppressive therapy, plasmapheresis or dialysis
- Pre-specified adverse event or laboratory abnormality that, per Protocol, requires permanent discontinuation of study CCX140-B
- Any other treatment-related adverse event, laboratory evidence of toxicity or intolerance that in the judgment of the investigator, warrants permanent discontinuation of CCX140-B

Halt treatment then alert sponsor and reassess after 1 week when there is a Clinical diagnosis of hemolysis in the judgment of the investigator, based on elevation of LDH, elevation of reticulocyte count, elevation of bilirubin and or other laboratory indications.

Consider discontinuation of treatment when a subject experiences any of the following events:

An increase of serum ALT to >3xULN should be followed by repeat testing within 48 to 72 hours of all four of the usual serum measures (ALT, AST, ALP, and TBL) to confirm the abnormalities and to determine if they are increasing or decreasing.

Discontinuation of treatment should be considered if:

- ALT or AST  $>8\times$ ULN
- ALT or AST  $>5\times$ ULN for more than 2 weeks
- ALT or AST  $>3\times$ ULN and (TBL  $>2\times$ ULN or INR  $>1.5$ )
- ALT or AST  $>3\times$ ULN with the appearance of fatigue, nausea, vomiting, right upper quadrant pain or tenderness, fever, rash, and/or eosinophilia ( $>5\%$ )

Halt treatment then alert sponsor and reassess after 2 weeks whenever a subject has either

- Hemoglobin reduced from baseline by  $\geq 2$  g/L and deemed clinically significant by the PI
- An increase in reticulocyte count by  $\geq 2\%$  (absolute) from baseline that is not otherwise explained
- $\geq$  moderate symptoms limiting instrumental activities of daily living or asymptomatic (based on diagnostic evaluation only) and deemed clinically significant by the investigator
- Any adverse events assessed as moderate, related to study drug, and clinically significant

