### **Dose Modification / Stopping Rules for the overall study**

A dose will be considered as potentially exceeding the maximum tolerated dose should any of the following events occur:

- 2 or more subjects with confirmed QTcF prolongation  $\geq 450$  msec and an increase from baseline of  $\geq 30$  msec, based on triplicate 12-lead ECGs that is not otherwise explained
- 2 or more subjects with clinically significant hemolytic anemia, defined as hemoglobin that has declined from baseline by at least 2 grams/deciliter and is less than or equal to 8 g/dL and is assessed by the investigator and is not otherwise explained
- 2 or more subjects with bilirubin greater than 3 times upper limit of normal, and not ascribable to Gilbert's disease
- 2 or more subjects with new motor neuropathy or sensory neuropathy that limits instrumental activities of daily living and is assessed by the Investigator as clinically significant
- 2 or more subjects who require dose reduction or discontinuation due to adverse events assessed as possibly related to Study Drug, where the adverse events are medically similar events in the same System Organ Class based on MedDRA criteria

If a dose is assessed to be above the maximum tolerated dose, dosing will be reduced to the next lower dose.

A Safety Review Committee (SRC) comprising the Sponsor Study Director, Medical Monitor, at least one external expert nephrologist, and the Study Statistician will review all safety events described in the dose modification rules and all serious adverse events as they occur. The SRC will periodically review all adverse events and all laboratory abnormalities. The SRC may declare a dose to be above the maximally tolerated dose based either on the defined rules or on other considerations.

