11. Participated in any clinical study of an investigational product within 12 weeks prior to screening or within 5 half-lives after taking the last dose
12. Currently on dialysis or likely to require dialysis during the study.
13. History or presence of any form of cancer within the 5 years prior to screening, with the exception of excised basal cell or squamous cell carcinoma of the skin, or carcinoma *in situ* such as cervical or breast carcinoma *in situ* that has been excised or resected completely and is without evidence of local recurrence or metastasis
14. Positive HBV, HCV, or HIV viral screening test. Subjects who have received highly effective therapy for HCV demonstrated to have negative viral titers for at least 6 months following discontinuation of treatment, will be considered to have a negative HCV screening test weeks prior to screening
15. Evidence of tuberculosis based on interferon  $\gamma$  release assay (IGRA), tuberculin purified protein derivative (PPD) skin test, or chest radiography done during screening or within 6 weeks prior to screening
16. Evidence of hepatic disease; AST, ALT, alkaline phosphatase  $>2 \times$  ULN, or total bilirubin  $>2 \times$  ULN or INR  $> 1.5 \times$  ULN at screening with the exception that isolated INR elevation in

the absence of other significant liver enzyme abnormalities is explained by anticoagulant therapy, (e.g. warfarin).

17. Clinically significant peripheral neuropathy
18. Hematologic abnormalities as follows: Hb <8 g/dL, platelets <50,000, ANC <1000 cells/ $\mu$ L) at baseline
19. Abnormality of ECG at screening, assessed by the Investigator as clinically significant (e.g. QTcF greater than 450 msec).
20. History of alcohol or illicit drug abuse. Recreational use of cannabis is not excluded where legalized.
21. History of gastrointestinal conditions that may interfere with study medication compliance, e.g., severe gastroparesis, with regurgitation of food or oral medication
22. Known hypersensitivity to CCX140-B or inactive ingredients of the CCX140-B tablets (including microcrystalline cellulose, starch, crospovidone, magnesium stearate, or silicon dioxide)
23. Renal disease associated with disorders other than FSGS (e.g. lupus nephritis, C3 glomerulonephropathy) that is active, or has significant risk of progressing to end stage renal disease during the 12-week initial treatment phase of the study

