#### 7.5. Dose Modification Rules

**Table 2: Dose Modification Rules for Individual Subjects**

Assessment	Event	Timing	Response
Serum Creatinine	50% increase from baseline value	If confirmed by repeat measurement after 2 weeks	If confirmed by repeat measurement after 2 weeks
Urine Protein:Creatinine ratio (UPCR)	If baseline UPCR < 6.0 g/g an increase of > 3.0 g/g; if UPCR $\geq$ 6.0 g/g an increase of 50%	If confirmed by repeat measurement after 2 weeks	If confirmed by repeat measurement after 2 weeks
ALT, AST	ALT or AST $\geq$ 8x ULN	Confirmed within 72 hours (ALT, ASP, ALP and Total Bilirubin should all be re-tested)	Consider Discontinuation of Treatment
ALT, AST	ALT or AST $\geq$ 5x ULN	Confirmed within 2 weeks (ALT, ASP, ALP and Total Bilirubin should all be re-tested)	Consider Discontinuation of Treatment
ALT, AST, Total	ALT or AST $\geq$ 3x	Confirmed within 72	Consider Discontinuation of

Bilirubin and INR	ULN and Total Bilirubin > 2 ULN or INR > 1.5	hours (ALT, ASP, ALP, Total Bilirubin and INR should all be re-tested)	Treatment
ALT, AST	ALT or AST $\geq$ 3x ULN with the appearance of fatigue, nausea, vomiting, right upper quadrant pain or tenderness, fever, rash and /or eosinophilia (>5%)	Confirmed within 72 hours (ALT, ASP, ALP and Total Bilirubin should all be re-tested)	Consider Discontinuation of Treatment
Hemolysis	Clinical diagnosis of hemolysis in the judgment of the investigator, based on elevation of LDH, elevation of reticulocyte count, elevation of bilirubin and or other laboratory indications.	Halt treatment then reassess after 1 week	If normalized, continue to treat at reduced dose, defined as the next lower dose. Otherwise, contact Medical Monitor to discuss next steps
Anemia	Hemoglobin reduced from baseline by $\geq$ 2 g/L and deemed clinically significant by the PI	Halt treatment then reassess after 2 weeks	If normal, continue to treat at reduced dose, defined as next lower dose. Otherwise, contact Medical Monitor to discuss next steps
Reticulocyte Count	Increase in reticulocyte count by $\geq$ 2% (absolute) from baseline that is not otherwise explained	Halt treatment then reassess after 2 weeks	If within normal range for the hematocrit, continue to treat at reduced dose, defined as next lower dose. Otherwise, contact Medical Monitor to discuss next steps

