Peripheral Neuropathy	$\geq$ moderate symptoms limiting (limiting instrumental activities of daily living or asymptomatic (based on diagnostic evaluation only) and deemed clinically significant by the investigator	Halt treatment then reassess after 2 weeks	Contact Medical Monitor to discuss next steps
Other Clinically Significant Events	Any adverse events assessed as moderate, related to study drug, and clinically significant	Halt treatment then reassess after 2 weeks	Contact Medical Monitor to discuss next steps

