### **7.5.1. Dose Modification / Stopping Rules for the Overall Study**

A dose will be considered as potentially exceeding the maximum tolerated dose and consideration will be given for stopping the study should any of the following events occur:

- 2 or more subjects with QTcF prolongation  $\geq$  450 msec and an increase from baseline of  $\geq$  30 msec, based on triplicate 12-lead ECGs that is not otherwise explained
- 2 or more subjects with clinically significant hemolytic anemia, defined as hemoglobin that has declined from baseline by at least 2 grams/deciliter and is less than or equal to 8 g/dL and is assessed by the investigator and is not otherwise explained
- 2 or more subjects with bilirubin greater than 3 times upper limit of normal, and not ascribable to Gilbert's disease
- 2 or more subjects with new motor neuropathy or sensory neuropathy that limits instrumental activities of daily living and is assessed by the Investigator as clinically significant
- 2 or more subjects who require dose reduction or discontinuation due to adverse events assessed as possibly related to Study Drug, where the adverse events are medically similar in the same System Organ Class based on MedDRA criteria.

If a dose is assessed to be above the maximally tolerated dose, dosing and dose escalation will be limited to the next lower dose.

A Safety Review Committee (SRC) comprising the Study Director, Medical Monitor, Clinical Pharmacologist, at least one external expert nephrologist, and Study Statistician will review all safety events described in the stopping rules and all serious adverse events as they occur. The SRC will periodically review all adverse events and all laboratory abnormalities. The SRC may declare a dose to be above the maximally tolerated dose based on the defined rules, or based on other considerations.

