## 1 INTRODUCTION

The purpose of this Statistical Analysis Plan (SAP) is to provide a description of the statistical methods to be implemented for the analysis of data from the study with protocol number CL012\_140. This document is based on protocol amendment 1.0 (17APR2018) and Case Report Form (CRF) version 8.0 (02APR2020). The statistical definitions and analytical methods described in this SAP supersede that in the protocol. The SAP will be finalized prior to database lock. Any deviations from the SAP after database lock will be documented in the final Clinical Study Report (CSR).

Following study CL011\_140, a randomized, double-blind, placebo-controlled dose-ranging study to evaluate the safety and efficacy of CCX140-B in subjects with Focal Segmental Glomerulosclerosis (FSGS), its results did not support the development of CCX140 in FSGS. Therefore a decision was made to not continue enrollment in study CL012\_140, which also investigates CCX140 in patients with FSGS and nephrotic syndrome. In addition, the efficacy and safety summaries will be limited to specific parameters and an abbreviated CSR will be developed for this study. See further details in Section 6, Changes From Protocol-Specified Statistical Analyses.

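### The individual-subject anemia halt rule is printed as a hemoglobin fall of 2 g/L (0.2 g/dL), very probably a unit error for 2 g/dL; the sponsor should confirm the intended value

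*Protocol*

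**What the plan says.** The individual rule appears twice in the protocol. The Anemia row of Table 2 (Section 7.5) sets the trigger at a fall from baseline of at least "2 g/L and deemed clinically significant by the PI". The synopsis rule for individual subjects ends in the same unit and the same condition: "g/L and deemed clinically significant by the PI". Both parts are needed, the numeric fall and the PI's view that it matters clinically. Once they are met, drug is stopped and the subject is reassessed two weeks later. Table 2 then resumes treatment one dose level down if the value is normal, and otherwise refers the case to the Medical Monitor.

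The other hemoglobin limits are these:

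- Study-level rule, synopsis: "2 or more subjects with clinically significant hemolytic anemia, defined as hemoglobin that has declined from baseline by at least 2 grams/deciliter".
- Study-level rule, Section 7.5.1: "hemoglobin that has declined from baseline by at least 2 grams/deciliter and is less than or equal to 8 g/dL".
- Eligibility, exclusion 18 in the synopsis and in Section 4.3: "Hematologic abnormalities as follows: Hb <8 g/dL".

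On what follows a dose reduction, the Day 71 row of Table 1 allows escalation only if "Subject did not require previous downward dose adjustment". The extension rules (synopsis and Section 3.1.2) repeat that condition. The Day 43 row of Table 1 does not have it. The schematic text in SAP Section 2.2.1, for Day 71 onward, refers instead to a previous down-titration from 15 mg BID.

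**The concern.** A limit of 0.2 g/dL is very small for a laboratory value that varies from draw to draw, and it stands alone among limits given in g/dL. The study-level rule uses the same numeral, 2, for the same quantity, a fall from baseline, with the other unit.

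Anemia is one of the two nonclinical findings of concern in Section 1.3 and is expected to carry over to humans, so this rule may well be used. If the numeric part filters nothing, the halt becomes a matter of individual PI judgment. A halt that was not needed costs the subject two weeks off drug and then a lower dose. Under the protocol's wording, it also closes off later escalation in an intra-subject dose-escalation study.

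**Working it through.** No sample size, power or error rate in the documents depends on this value, so there is no planned figure to reproduce. The check is a unit conversion, a comparison of the limits, and two short calculations.

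**1. Conversion.** 1 g/dL = 10 g/L, so 2 g/L = 2/10 = 0.2 g/dL. The study-level fall of 2 g/dL is 2/0.2 = 10 times larger.

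**2. Relative size.** At the lowest eligible hemoglobin, 8 g/dL, the printed fall is 0.2/8 = 2.5%, against 2/8 = 25% for 2 g/dL. At 12 g/dL the figures are 0.2/12 = 1.7% and 2/12 = 16.7%.

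**3. Limits side by side.**

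| Place | Limit | Unit printed |
|---|---|---|
| Individual rule, synopsis and Table 2 | fall of at least 2 | g/L |
| Study-level rule, synopsis and 7.5.1 | fall of at least 2, and value of 8 or less | g/dL |
| Exclusion 18, synopsis and 4.3 | below 8 | g/dL |

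The g/L unit is printed in two separate places, so a PDF reading fault is unlikely. Neither the protocol nor the SAP gives a reason for a 0.2 g/dL trigger.

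**4. How much the numeric part screens out (illustration).** Take a subject whose true hemoglobin does not change, with independent normal variation of the same SD at baseline and at the visit. The chance of an apparent fall of at least d at one visit is P(Z > d/(SD × √2)). The documents give no SD; the range below is an assumption.

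| Assumed within-subject SD (g/dL) | d = 0.2 g/dL | d = 2 g/dL |
|---|---|---|
| 0.2 | 0.240 | < 0.001 |
| 0.3 | 0.319 | < 0.001 |
| 0.5 | 0.389 | 0.002 |
| 0.7 | 0.420 | 0.022 |

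So 24 to 42% of stable subjects would meet the printed number at a single visit, against about 2% or fewer for 2 g/dL. These are chances of meeting the numeric half of the rule. They are not halt rates, because the PI must also judge the fall significant.

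**5. Direction of the error.** Any fall of 2 g/dL or more is also a fall of 0.2 g/dL or more. With the same PI clause, the printed rule catches every case that a 2 g/dL rule would catch.

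**6. What the corrected limit would do.** For baseline B (g/dL), a 2 g/dL rule is reached at B − 2. Both hemoglobin parts of the study-level rule are met at the smaller of B − 2 and 8.

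| B | Individual halt reached at | Study-level hemoglobin parts met at | Gap |
|---|---|---|---|
| 8 | 6 | 6 | 0 |
| 9 | 7 | 7 | 0 |
| 10 | 8 | 8 | 0 |
| 11 | 9 | 8 | 1 |
| 12 | 10 | 8 | 2 |

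For subjects who enter at 8 to 10 g/dL, the corrected limit is therefore reached only at 8 g/dL or less.

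**The case against.** The strongest reply is that the PI clause contains the error. A trivial fall halts nothing unless a PI calls it clinically significant, and the documents give no basis for saying that any PI would. Other Table 2 rows already stop treatment for hemolysis, for an unexplained reticulocyte rise, and for "Any adverse events assessed as moderate, related to study drug, and clinically significant". The Safety Review Committee also reviews laboratory abnormalities. All of this stands, and it limits the point to a minor one. It does not make the printed number right.

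Four stronger readings are tempting, and the documents do not support them:

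- *The individual and study-level rules contradict each other.* They do not. One acts on a single subject, the other on two or more subjects with unexplained hemolytic anemia, and the first may properly be stricter. The case for a slip rests on the unit and the shared numeral.
- *A quarter or more of stable subjects would be taken off drug.* The percentages above cover only the numeric half and rest on an assumed SD.
- *Any resulting dose reduction rules out later escalation.* That holds under the protocol's Day 71 and extension wording. The SAP schematic ties the bar to down-titration from 15 mg BID, so a subject reduced from 10 to 5 mg BID is not clearly barred under that text, and the Day 43 row has no bar.
- *Two such reductions would mark the dose as above the maximum tolerated dose.* That rule needs medically similar adverse events judged possibly related to drug, and the committee decides. A small laboratory fall alone does not meet it.

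**Conclusion.** The printed unit is very probably wrong, and 2 g/dL is the likely intent. This is an inference from the other limits, so the sponsor has to confirm it. As printed, the threshold is ten times smaller than the study-level fall, and the numeric limit does almost no screening at any SD in the assumed range of 0.2 to 0.7 g/dL.

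The severity is minor. The error is in the cautious direction, misses no true anemia that the corrected rule would find, and enters no efficacy analysis. How many unneeded halts it caused, if any, cannot be worked out from the documents. A reader might infer that subjects were put at risk; the containment in step 5 of the working shows that the printed rule is the more protective of the two. The SAP also reports of this trial: "Therefore a decision was made to not continue enrollment in study". Little of the harm can therefore still be prevented.

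**What to change.** 1. The sponsor confirms the intended value. If it is 0.2 g/dL, the protocol should say why.
2. If it is 2 g/dL, change g/L to g/dL in the synopsis rule and in the Anemia row of Table 2, and keep the PI clause. This restores a working numeric limit but does not remove differences between PIs.
3. Accept one downside knowingly: subjects entering at 8 to 10 g/dL would reach the corrected limit only at 8 g/dL or less. The hemolysis, reticulocyte and moderate-event halts and committee review still apply to them.
4. The documents do not say whether anyone remains on drug. Notify any site still treating subjects. If there is none, record the correction in the abbreviated CSR and check the listings for halts or reductions for anemia at a fall below 2 g/dL. The check is indirect. The SAP lists action taken for each adverse event (Section 3.6.1) and dose level per dispensing record (Section 3.3.8), but names no field for the Table 2 row behind a halt.

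The cost is one confirmation and one unit changed in two places, plus either a letter to active sites or a CSR note with a listing check of at most 13 subjects (SAP Section 3.4.3).

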### **7.5.1. Dose Modification / Stopping Rules for the Overall Study**

A dose will be considered as potentially exceeding the maximum tolerated dose and consideration will be given for stopping the study should any of the following events occur:

- 2 or more subjects with QTcF prolongation  $\geq$  450 msec and an increase from baseline of  $\geq$  30 msec, based on triplicate 12-lead ECGs that is not otherwise explained
- 2 or more subjects with clinically significant hemolytic anemia, defined as hemoglobin that has declined from baseline by at least 2 grams/deciliter and is less than or equal to 8 g/dL and is assessed by the investigator and is not otherwise explained
- 2 or more subjects with bilirubin greater than 3 times upper limit of normal, and not ascribable to Gilbert's disease
- 2 or more subjects with new motor neuropathy or sensory neuropathy that limits instrumental activities of daily living and is assessed by the Investigator as clinically significant
- 2 or more subjects who require dose reduction or discontinuation due to adverse events assessed as possibly related to Study Drug, where the adverse events are medically similar in the same System Organ Class based on MedDRA criteria.

If a dose is assessed to be above the maximally tolerated dose, dosing and dose escalation will be limited to the next lower dose.

A Safety Review Committee (SRC) comprising the Study Director, Medical Monitor, Clinical Pharmacologist, at least one external expert nephrologist, and Study Statistician will review all safety events described in the stopping rules and all serious adverse events as they occur. The SRC will periodically review all adverse events and all laboratory abnormalities. The SRC may declare a dose to be above the maximally tolerated dose based on the defined rules, or based on other considerations.

